7.3 TREATMENT COMPLIANCE

Treatment compliance (see [Section 5.4.4](#) for the definition and calculation) will be summarized for the SAF using descriptive statistics (N, mean, SD, minimum, median, maximum) for day 1, maintain period and overall treatment period. The number and percentage of patients with the following overall compliance categories will be presented:

- "<80% of planned",
- "80 to 120% of planned" and
- ">120% of planned".

7.4 PRIMARY OBJECTIVE ANALYSIS

Refer to [Section 7.8.1](#) for the description for adverse events including the primary endpoint.

7.5 SECONDARY OBJECTIVE ANALYSIS

7.5.1 Key secondary objective analysis

This section is not applicable as no key secondary endpoint has been specified in the protocol.

7.5.2 Secondary objective analysis

For continuous secondary endpoints, the primary analysis will implement the hybrid strategy (EC-H) of handling ICE defined in [Section 6.3](#). Any data collected after the ICE will be censored for the timepoint afterwards, i.e., only data prior to the ICE will be considered.

Descriptive summaries and graphical displays (line plots) will be produced using OC method for continuous secondary endpoints and binary secondary endpoints respectively.

7.6 FURTHER OBJECTIVE ANALYSIS

Analysis of further endpoints is described in Section 7.2.4 of the CTP. All analyses of further endpoints will be performed for the SAF.

7.6.1 Further efficacy endpoints

For each of the further endpoint described below, hybrid strategy will be used to handle intercurrent events which lead to data censoring as described for the primary endpoint.

Continuous further endpoints

The further continuous and binary endpoints will be evaluated in a descriptive manner using OC method as section 7.2.4 in CTP, by visit if applicable.

Questionnaires will be descriptively summarized by visit.

Binary further endpoints

Descriptive statistics will be displayed based on the OC-NRI approach for each of the binary further endpoint, by visit if applicable.

7.6.2 Use of rescue therapy

Summary of use of rescue therapy

Frequency of use of rescue therapy, as identified on the eCRF, from Day 1 up to the end of reporting period, will be summarized with the number and percentage of patients by preferred name.

Time to first use of rescue therapy

The time to event will be defined as the start date of first rescue therapy use minus the date of first drug administration, plus 1 day. If patient has no rescue therapy, the time to first use of rescue therapy will be censored on the patient level at the last contact day up to the end of reporting period.

A Kaplan-Meier analysis of time to the first use of rescue therapy will be presented. KM-estimates of the survival/failure probabilities at weekly intervals, as well as the median time-to-event will be provided. Confidence intervals will be based on two-sided $\alpha=0.05$.

7.6.3 Other analysis

Since there's dose modification at week [REDACTED] and re-assessment week [REDACTED] according to the Table 3.1: 1 in CTP, descriptive summaries for the status of HS-PGA grade change at Week [REDACTED] and Week [REDACTED] by responder status at baseline will be provided.

7.7 EXTENT OF EXPOSURE

An overall table will summarize the entire treatment period. The number of subjects who received a dose of trial drug will be tabulated. Treatment exposure will be assessed as the total dose of treatment [mg] administered for the loading stage, the maintenance stage, as well as the overall dose across the two stages, which will be summarised by descriptive statistics (N, mean, SD, minimum, median, maximum). The total duration of exposure [days] will also be displayed.

7.8 SAFETY ANALYSIS

All safety analyses will be performed on the safety analysis set.

All safety analyses will be performed following BI standards for overall on-treatment period. No hypothesis testing is planned. OC-IR and OR methods will be used for safety reporting. AE and possibly clinically significant laboratory abnormalities will be analysed under OR (as defined in [Section 6.6.3](#)); the safety data by visit, i.e., laboratory, vital signs and local tolerability, will be analysed under OC-IR (as defined in [Section 6.6.3](#)).

As the onset time of an AE will not be collected in the trial, any AE which occurs on the same day as a treatment dose will be assigned to the "post treatment". For safety assessments by visits, if time is not collected, data on the same day of a treatment dose will be treated to be "prior treatment" except for scheduled local tolerability and post-dose vital signs assessments.

Off-treatment data will be listed only.

7.8.1 Adverse Events

AEs will be coded with the most recent version of MedDRA.

For AEs in current trial, we will summarize AEs start in 1368-0052 and still ongoing in current trial 1368-0067 plus new AEs start in current trial.

The analyses of AEs will be descriptive in nature. All analyses of AEs will be based on the number of patients with AEs and not on the number of AEs. System organ classes (SOC, if applicable) will be sorted according to the standard sort order specified by the EMA, preferred terms (PT, if applicable) will be sorted by total frequency (within SOC).

For details on summarization of AE data, please refer to "Handling and summarization of adverse event data for clinical trial reports and integrated summaries" ([15](#)) and "Handling of missing and incomplete AE dates" ([10](#)).

The analysis of AEs will be based on the concept of TEAEs. This means that all AEs will be assigned to the screening period, on-treatment period (i.e. treatment phase plus REP) or off-treatment period (i.e. follow up) as defined in [Section 6.1](#). Since only the start date of an AE is collected (without start time), any AE occurrence on the same day as the first spesolimab administration will be assigned to the on-treatment phase.

Exposure-adjusted adverse event incidence rates for TEAE will be calculated using the following approach:

- 1) The exposure adjusted incidence rate (per 100 subject years) of a selected TEAE is defined as the number of subjects experiencing the adverse event per treatment group during time at risk divided by the total time of subjects at risk to contribute the event to the analysis multiplied by 100 (per 100 subject years), where:

Time at risk [subject years] = (date of onset of AE – first treatment start date in current study +1) / 365.25

- 2) If, for a subject, the selected TEAE didn't occur, then the time at risk will be censored at min (date of death, last contact date per EoS page, cut-off date for the interim analysis, or the end of on-treatment period). For each selected TEAE, the exposure adjusted incidence rate will be calculated as:

Incidence rate [1/100 Subject years (pt-yrs)] = 100 * number of subjects with TEAE / Total TEAE-specific time at risk [subject years].

An overall summary of AEs will be presented. This overall summary will include summary statistics for the class of other significant AEs (sponsor definition based on ICH E3) and for the class of AESIs.

The following is considered an AESI in this trial:

- Systemic hypersensitivity including infusion reaction and anaphylactic reaction
- Severe infections (according to RCTC grading)
- Opportunistic and mycobacterium tuberculosis infections
- Hepatic injury
A hepatic injury is defined by the following alterations of hepatic laboratory parameters:
 - an elevation of AST (aspartate aminotransferase) and/or ALT (alanine aminotransferase) ≥ 3 -fold ULN combined with an elevation of total bilirubin ≥ 2 -fold ULN measured in the same blood draw sample, or in samples drawn within 30 days of each other
 - OR
 - aminotransferase (ALT, and/or AST) elevations ≥ 10 -fold ULN.

In addition, user defined adverse event concepts (UDAEC) identified through specific search criteria will be reported separately (see [Table 7.8.1: 1](#))

Table 7.8.1: 1 Project MEDDRA search criteria for User Defined Adverse Events Concepts

User-defined AE category		
	Label	Description
Hypersensitivity	Hypersensitivity ALL	Combined search strategy based on the three individual UDAECs described below
	Anaphylactic reaction, narrow	Narrow SMQ "Anaphylactic reaction"
	Angioedema, narrow	Narrow SMQ "Angioedema"
	Hypersensitivity, narrow	Narrow SMQ "Hypersensitivity"
Infections (serious/severe, opportunistic)	Infections 'ALL'	terms from combined search with sort order # in (20, 30, 40, 21, 22) Sort order if applicable to project or trial
	Opportunistic infections	SMQ "Opportunistic infections", narrow
	Tuberculosis infections	sub-BICMQ "Tuberculosis related terms", narrow BICMQ "Infections", sub-search 8.2 "Tuberculosis related terms" narrow
	Severe infections	SOC "Infections and infestations" with AETOXGR >= 3 OR AESEV = 'Severe'. Not derived for studies where both severity variables are collected. SOC "Infections and infestations" of at least severe RCTC grade (>= 3) or any severe events
	Serious infections	SOC "Infections and infestations" with [AECOD: AESER = 1] SOC "Infections and infestations" with "intensity= serious"
Malignancies	Malignant tumours	sub-SMQ "Haematological malignant tumours", narrow, sub-SMQ "Non-Haematological malignant tumours", narrow
	Malignancies excluding NMSC	sub-SMQ "Malignant tumours" excluding terms from search with sort order #=340 Sub-SMQ "Malignant tumours" excluding NMSC, where NMSC is defined above
Torsades de Pointes	Torsades de Pointes	Broad sub-SMQ "Torsade de pointes/QT prolongation"
Depression	Depression	sub-SMQ "Depression (excl suicide and self-injury)", broad

User-defined AE category		
	Label	Description
Suicidal ideation and behavior (SIB)	sub-SMQ "Suicide/self-injury"	
DRESS	DRESS (Drug reaction with eosinophilia and systemic symptoms syndrome), broad	SMQ "Drug reaction with eosinophilia and systemic symptoms syndrome", broad Algorithm: A or (B and C and D) or (B and C and E) or (B and D and E)
	DRESS (Drug reaction with eosinophilia and systemic symptoms syndrome), narrow	SMQ "Drug reaction with eosinophilia and systemic symptoms syndrome", narrow Only category A

* this is achieved by retrieving all cases found either by running subsearch 1 in narrow scope (BICMQ search ID 32019093) or subsearch 2 (BICMQ search ID 32019094)

The frequency of patients with AEs will be summarised by prior treatment from parent trial, primary SOC and PT. AEs which were considered by the investigator to be drug related will be summarised separately. Separate tables will also be provided for patients with SAEs, patients with AESIs, patients with AE leading to discontinuation of the trial medication, and patients with other significant AEs (as described previously). AEs will also be summarized by maximum intensity.

For disclosure of AE data on ClinicalTrials.gov, the frequency of patients with non-serious AEs occurring with an incidence of greater than 5% (in PTs) will be summarised by treatment, primary SOC and PT. The frequency of patients with SAEs and drug related SAEs will also be summarised respectively.

For disclosure of AE data in the EudraCT register, the frequency of non-serious AEs with an incidence of greater than 5 % (in PTs) and the frequency of SAEs will be summarised.

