4. CHANGES IN THE PLANNED ANALYSIS OF THE STUDY

All analyses stated in the CTP (latest version) will be performed as planned with the following adaptations.

Considering the categorical nature of PGI-S and PGI-C, the frequency over time will be presented for these further endpoints instead of absolute change from baseline as planned in CTP.

The below further efficacy endpoints, which were not specified in the CTP, have been added:

- Percent change from baseline (%) in total abscess and draining fistula (AdT) count over time.
- Percent change from baseline (%) in total abscess, inflammatory nodule and draining fistula/tunnel (ANdT) count over time.
- Proportion of patients with achievement of m-HiSCR response over time.
- Proportion of patients with achievement of IHS4-55 response over time.
- Percent change from baseline (%) in total inflammatory nodule count up over time.
- Percent change from baseline (%) in total abscess count up to over time.
- Achievement of complete elimination of draining fistulas over time.
- Achievement of complete elimination of abscess over time.
- Proportion of patients with achievement of HiSCR over time.
- At least 30% reduction from baseline in Numerical Rating Scale (NRS30) in Patient's Global Assessment of HS Pain over time.

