6. GENERAL ANALYSIS DEFINITIONS

6.1 TREATMENT(S)

For basic study information on the treatment to be administered, assignment to treatment, and selection of dose, cf. Section 4 of the CTP.

The study phases are defined relative to first dose at Day 1 as below:

Table 6.1: 1 Flow chart of analysis phases of the study

Study analysis phase	Description	Start (included)	End (included)
Screening phase	Screening	Earliest of (Date of informed consent, first screening procedure)	Date/time of start of the first study dose minus 1 second.
Treatment phase & Residual effects period	On-treatment period	Date/time of start of the first study dose regardless of infusion or injection (Day 1)	Earliest of: i) Date of last study drug regardless of infusion or injection + 112 days at 23:59, ii) cut-off for interim analysis if applicable.
Follow-up phase ¹ (if applicable)	Off-treatment period (if applicable)	Date of end of last study dose + 113 days at 0:00 a.m.	Latest of: i) Date of EOS visit; ii) last contact date on trial termination page at 11:59 p.m.

Dates are defined individually per patient. If more than one date is associated with a specific visit, measurements associated with a specific date are assigned to a study analysis phase according to the rules specified in the table. An analysis phase will not extend beyond the start date of the following phase.

¹ The off-treatment period (i.e. Follow-up phase) only exists if the date of EoS visit or the last contact date is after the date of end of last administration + 112 days.

Treatments will be labelled for final analysis as follows:

Tables will be displayed also by prior treatment from parent trial for final analysis:

- “Prior Placebo” (applicable to analysis for whole on-treatment period, i.e., including infusion loading at Day 1 for placebo patients from parent trial]
 - “Prior Placebo + uptitration at Week [] (applicable to analysis for whole on-treatment period, i.e., including infusion loading at Day 1 for placebo patients from parent trial and after dose escalation]
 - “Prior Placebo + Other” (applicable to analysis for whole on-treatment period, i.e., placebo patients from parent trial who received [] dose [] during all [] period or who were early discontinued before Week [])

- “Prior Speso” (applicable to analysis for whole on-treatment period, i.e., including [REDACTED] at Day 1 for speso patients from parent trial, before and post dose escalation)

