6.7 BASELINE, TIME WINDOWS AND CALCULATED VISITS

Measurements reported with date and time and taken prior to start of administration of trial treatment will be considered pre-treatment values. Measurements reported with a date only (and no time) and taken on the day of first administration of trial treatment will also be considered pre-treatment values. These pre-treatment values will be assigned to visits according to the nominal visit number as recorded on the eCRF or as provided by the laboratory.

Baseline, unless otherwise specified, is defined as the last measurement collected prior to the start of administration of the trial treatment.

For the baseline defined in efficacy endpoints like “change from baseline” or “compared to baseline”, unless otherwise specified, is defined as the last measurement before initiation of treatment (cf. [Section 5](#)).

Baseline for time to event endpoints, is defined as the last measurement collected prior to the start of administration of the trial treatment in the current extension trial 1368-0067.

For analysis of anti-drug antibodies (ADA), 2 different baselines will be used for the clinical trial report (CTR). For the analysis of ADA impact on pharmacokinetic (PK), the entire course of treatment is to be considered and assessments prior to initial trial of the parent trial (1368-0052) is considered baseline. Details will be discussed on the trial CTR.

For the analysis of ADA impact on safety and efficacy endpoints, baseline is defined as the first evaluable sample collected prior to treatment administration at baseline of this trial 0067.

Measurements taken after start of administration of trial treatment will be considered either on- or off-treatment values based on the definition in [Section 6.1](#), and will be assigned to visits for statistical analysis, if applicable, as defined below.

Analysis of AE data, potentially clinically significant abnormal laboratory values, concomitant medication or non-drug therapies, as well as use of rescue therapy will not be based on visits. Frequency tables for these data will be using on-treatment data and categorized based on their occurring/starting dates. Therefore, no assignment to time windows will be necessary for such data.

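### SAP 7.8.1, which carries the primary endpoint, says parent-trial AEs that are merely still ongoing will be summarised with new AEs; read literally, this conflicts with the protocol's TEAE definition and the SAP's own on-treatment rules

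*SAP*

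**What the plan says.** **SAP.** Section 7.4 contains no analysis of its own. It refers to section 7.8.1 "for the description for adverse events including the primary endpoint". Near its start, section 7.8.1 says that for AEs in the current trial "we will summarize AEs start in 1368-0052 and still ongoing in current trial 1368-0067 plus new AEs start in current trial". The only condition placed on a parent-trial AE is that it has not ended.

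Other SAP rules bear on the same tables:

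- Table 6.1: 1 starts the on-treatment period at "Date/time of start of the first study dose regardless of infusion or injection (Day 1".
- Section 6.7, covering AEs among other data, says: "Frequency tables for these data will be using on-treatment data and categorized based on their occurring/starting dates".
- Section 7.8: "All safety analyses will be performed following BI standards for overall on-treatment period".
- Section 7.8.1, a few paragraphs after the disputed sentence: "The analysis of AEs will be based on the concept of TEAEs".
- Section 7.8.1, on counting: "All analyses of AEs will be based on the number of patients with AEs and not on the number of AEs".
- Section 4, on departures from the protocol: "All analyses stated in the CTP (latest version) will be performed as planned with the following adaptations". None of the listed adaptations concerns AEs.

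**Protocol.** Section 7 limits the primary analysis to AEs whose onset lies between start of treatment and the end of the REP, 16 weeks after the last dose. Section 7.2.5 repeats this and adds one exception: an AE that began before first drug intake and got worse under treatment. Section 5.2.6.2.1 has ongoing parent-trial AEs entered again in the extension eCRF with their parent-trial details. If the intensity changes after first dose, the AE with its new intensity is entered as a new event.

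**The concern.** The trial has one primary endpoint, the occurrence of TEAEs, and the section that analyses it contains a sentence wider than the definition. An AE that began in 1368-0052 and continues unchanged is not treatment-emergent in 1368-0067 under the protocol, yet the sentence puts it in the same summary as new AEs.

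Two programmers working from this text could build different tables. One would apply the start-date filter and leave carry-overs out. The other would follow the scope sentence and count them. In the second case the tables that report the primary endpoint would include events that arose before the first extension dose. For patients from the parent placebo arm, those events could have begun before any spesolimab exposure. The tables shown by prior treatment would then present them as events on extension treatment.

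**Working it through.** The documents state no figure for this point, so there is none to reproduce. The check compares the rules and then works out what one patient is worth.

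**1. Where does an unworsened carried-over AE fall under each rule?**

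| Rule | Carried-over AE, no worsening |
|---|---|
| Protocol 7 (onset from first dose to end of REP) | Out |
| Protocol 7.2.5 (earlier onset only if it deteriorates) | Out |
| SAP Table 6.1: 1 with 6.7 (on-treatment, by start date) | Out |
| SAP 7.8 and the TEAE paragraph of 7.8.1 | Out |
| SAP 7.8.1 scope sentence, read literally | In |

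The start date decides this. Protocol 5.2.6.2.1 keeps the parent-trial information when the AE is re-entered, so the recorded onset precedes the first extension dose.

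**2. Is there another place for these AEs?** SAP 7.8.1 assigns every AE to screening, on-treatment or off-treatment. Screening starts at the earlier of consent and first screening procedure (Table 6.1: 1), so a parent-trial AE with an earlier onset fits no phase. Protocol 5.2.6.1.1 says such AEs are not to be recorded as baseline conditions. They therefore sit in the AE data, and the visible SAP text names no separate output for them.

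**3. Is worsening covered?** Yes. Worsening in intensity creates a new record under protocol 5.2.6.2.1, so the 7.2.5 exception can be met without counting the unchanged record.

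**4. Size per patient.** Input: about 45 patients (protocol synopsis). Tables count patients, so a carry-over adds to a term only when that patient has no new AE of the same term.

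- Overall column: 1/45 = 2.2 percentage points per added patient.
- Prior-treatment columns: the split is not given. Assuming 15 to 30 patients in a column, 1/15 = 6.7 points to 1/30 = 3.3 points.
- Registry display (SAP 7.8.1, non-serious terms above 5%): 2/45 = 4.4% and 3/45 = 6.7%, so three patients carry a term over the cut-off in a column of 45. The SAP does not say whether the cut-off applies overall or by group, so this is one case only.
- Overall proportion with any TEAE: it changes only for a patient with no new AE at all in the on-treatment period.

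**The case against.** The strongest defence is that the sentence only describes the record pool. It opens by speaking of AEs in the current trial, and it matches the eCRF collection rule in protocol 5.2.6.2.1: re-entered ongoing AEs plus new ones. Section 7.8.1 then applies the TEAE filter, SAP 5.1 keeps the primary endpoint as TEAEs, and SAP 4 says protocol analyses stand unless a change is listed. On that view the protocol definition governs and carry-overs drop out.

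Much of this stands. It means the SAP cannot be said to have redefined the endpoint. It does not settle the matter, because the sentence announces what will be summarised, not what is held in the database. The SAP also never restates the deterioration condition, and the frequency tables later in 7.8.1 are described by AEs, not TEAEs.

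Two limits on the evidence also stand. The SAP contents list runs from section 9 to section 11, so material that is not visible could contain an output for carry-overs. SAP 7.8.1 also refers summarisation details to sponsor standards that are not provided.

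A reader might infer that an AE which eases after first dose would be miscounted as treatment-emergent, since protocol 5.2.6.2.1 treats any changed intensity as a new event. The documents do not establish this. It would arise from the protocol's recording rule and not from the SAP sentence, protocol 7.2.5 admits earlier AEs only if they deteriorate, and the handling of linked records may be set in the sponsor standards. It forms no part of this point.

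**Conclusion.** The point holds as an internal conflict open to two readings. Read literally, the sentence gives a TEAE count wider than the protocol allows. Read as a pool definition, it is harmless but unstated. Nothing in the visible text tells a programmer which reading applies.

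The effect is small and descriptive. No hypothesis is tested, and each affected patient moves a term by about 2.2 percentage points, assuming about 45 treated patients. The by-term and prior-treatment tables are more exposed than the overall proportion. The number of carried-over AEs is not in the documents, so the total effect cannot be calculated.

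Two stronger readings are not supported:

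- **That the primary endpoint has been changed.** SAP 5.1 and SAP 4 say otherwise.
- **That the exposure-adjusted rates are wrong.** For an onset 30 days before first dose, the SAP formula would give (−30 + 1)/365.25 = −0.079 years at risk. But both documents define the rate for TEAEs only, so an unworsened carry-over should not enter it.

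**What to change.** Replace the scope sentence in SAP 7.8.1 with text such as:

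> AEs with onset in 1368-0052 that are ongoing at first dose in 1368-0067 and do not worsen under treatment are not TEAEs; they are excluded from the primary endpoint and TEAE tables and are shown in a separate table or listing. A carried-over AE counts as a TEAE only if it worsens after first dose (recorded as a new event under CTP 5.2.6.2.1), with onset at the date of worsening.

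If the wider scope is intended, declare it in SAP section 4 as a departure from protocol 7 and 7.2.5.

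The cost is SAP wording and one extra table or listing, or a flag in the AE listing already planned for Appendix 16.2. No new data are needed. Reported AE frequencies may be slightly lower than under the literal reading.

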5.2.6.1.4 Adverse events of special interest

The term AESI relates to any specific AE that has been identified at the project level as being of particular concern for prospective safety monitoring and safety assessment within this trial, e.g. the potential for AEs based on knowledge from other compounds in the same class. AESIs need to be reported to the sponsor’s Pharmacovigilance Department within the same timeframe that applies to SAEs, please see [Section 5.2.6.2.2](#).

The following are considered as AESIs:

Systemic hypersensitivity including infusion reaction and anaphylactic reaction

Any suspicion of severe infusion reaction systemic / hypersensitivity reaction and of any potential cases of anaphylaxis should be defined and assessed using the criteria discussed in the statement paper from Sampson HA ([Appendix 10.1 \[R11-4890\]](#)).

Severe infections

Refer to the RCTC grading in the ISF.

Opportunistic and mycobacterium tuberculosis infections

These include pneumocystis jirovecii, BK virus disease including PVAN, CMV, post-transplant lymphoproliferative disorder (EBV), progressive multifocal leucoencephalopathy, bartonellosis (disseminated only), blastomycosis, toxoplasmosis, coccidioidomycosis, histoplasmosis, aspergillosis (invasive only), candidiasis (invasive or pharyngeal), cryptococcosis, other invasive fungi (mucormycosis (zygomycosis, rhizopus, mucor, lichtheimia), scedosporium/pseudallescheria boydii, fusarium), legionellosis, listeria monocytogenes (invasive only), TB, nocardiosis, non-tuberculous mycobacterium, salmonellosis (invasive only), HBV reactivation, herpes simplex (invasive only), herpes zoster, strongyloides (hyperinfection syndrome and disseminated forms only), paracoccidioides, penicillium marneffeii, sporothrix schenckii, cryptosporidium species (chronic only), microsporidiosis, leishmaniasis (visceral only), trypanosoma cruzi infection (Chagas' disease) (disseminated only), campylobacteriosis (invasive only), shigellosis (invasive only), vibriosis (invasive due to vibrio vulnificus), hepatitis C virus progression [[R17-2617](#)].

Potential Severe DILI

A potential severe Drug Induced Liver Injury (DILI) that requires follow-up is defined by the following alterations of hepatic laboratory parameters:

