- An elevation of AST (Aspartate Aminotransferase) and / or ALT (Alanine Aminotransferase) ≥ 3 -fold ULN combined with an elevation of total bilirubin ≥ 2 -fold ULN measured in the same blood sample, or in samples drawn within 30 days of each other; or
- ALT and / or AST elevations ≥ 10 -fold ULN.

These lab findings constitute a hepatic injury alert and the patients showing these lab abnormalities need to be followed up according to the "DILI checklist" provided in the ISF.

In case of clinical symptoms of hepatic injury (icterus, unexplained encephalopathy, unexplained coagulopathy, right upper quadrant abdominal pain, etc.) without lab results (ALT, AST, total bilirubin) available, the investigator should make sure these parameters are analysed, if necessary, in an unscheduled blood test. Should the results meet the criteria of hepatic injury alert, the procedures described in the DILI checklist should be followed.

For patients with abnormal aminotransaminase levels between >1 and <3 x ULN at baseline:

1. An elevation of AST and / or ALT ≥ 3 -fold the baseline value combined with an elevation of bilirubin ≥ 2 -fold ULN or ≥ 2 -fold the baseline value (if bilirubin is elevated at baseline), measured in the same blood sample, or in samples drawn within 30 days of each other, or,
2. Aminotransferase elevations ≥ 5 -fold the baseline value.

For patients with abnormal aminotransaminase levels between ≥ 3 x ULN and <5 x ULN at baseline:

1. An elevation of AST and / or ALT ≥ 2 -fold the baseline value combined with an elevation of bilirubin ≥ 2 -fold ULN or ≥ 2 -fold the baseline value (if bilirubin is elevated at baseline); measured in the same blood sample or in samples drawn within 30 days of each other, or,
2. Aminotransferase elevations ≥ 3 -fold the baseline value.

Peripheral Neuropathy Any event suspected or diagnosed as Peripheral Neuropathy would be considered as an AESI. For the treatment interruption rules, please see [Section 4.2.1.4](#).

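### The SAP's AESI list leaves out peripheral neuropathy, which the protocol makes an AESI, and its hepatic definition drops the protocol's baseline-relative criteria; neither change is declared

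*SAP*

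**What the plan says.** Protocol 5.2.6.1.4 opens its list with "The following are considered as AESIs" and sets out five classes: systemic hypersensitivity, severe infections, opportunistic and tuberculosis infections, potential severe DILI, and peripheral neuropathy. On the last it says "Any event suspected or diagnosed as Peripheral Neuropathy would be considered as an AESI".

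SAP 7.8.1 opens with "The following is considered an AESI in this trial" and gives four classes. Peripheral neuropathy is not among them, and nothing marks the list as illustrative or refers the reader back to the protocol.

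Two outputs depend on the AESI class, both in SAP 7.8.1. The first is the overall AE summary ("An overall summary of AEs will be presented"), which is to include AESI statistics. The second is a dedicated table: "Separate tables will also be provided for patients with SAEs, patients with AESIs".

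SAP section 4 says "All analyses stated in the CTP (latest version) will be performed as planned with the following adaptations". The adaptations listed there concern the display of PGI-S and PGI-C and some added efficacy endpoints; none concerns AESIs.

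For the liver, the SAP gives two criteria, both in multiples of ULN. The protocol gives the same two and comments "These lab findings constitute a hepatic injury alert". It then adds further rules, each introduced by "For patients with abnormal aminotransaminase levels between", for baseline values of >1 to <3 x ULN and of 3 to <5 x ULN.

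**The concern.** The two documents define the same term differently, and the SAP is the one that will be programmed. Its footer is dated 2024 and the current protocol is dated July 2022, so the difference is not explained by the SAP having been written before neuropathy was added.

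At stake is the AESI reporting of a class the protocol singles out. Protocol Table 1.4.2:1 describes three cases reported by investigators as Guillain-Barré syndrome that an external panel thought better described as peripheral neuropathy, with a causal link judged unlikely. Section 4.2.1.4 is devoted to it. With about 45 patients, one or two events coded to different preferred terms would be easy to overlook in SOC/PT tables. The AESI table is the output that would bring them together.

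**Working it through.** **AESI classes side by side**

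| Class | Protocol 5.2.6.1.4 | SAP 7.8.1 |
|---|---|---|
| Systemic hypersensitivity | yes | yes |
| Severe infections | yes | yes |
| Opportunistic / TB infections | yes | yes |
| Hepatic injury / potential severe DILI | yes | yes, ULN criteria only |
| Peripheral neuropathy | yes | **no** |

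Protocol 5, SAP 4. The SAP adds no class of its own. The visible part of SAP Table 7.8.1:1 (user-defined AE concepts) shows no neuropathy concept. Such a row would not close the gap in any case, because those concepts are reported apart from the AESIs and do not define them.

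**Hepatic definition: isolated aminotransferase rise**

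Let b be baseline ALT or AST in multiples of ULN. The SAP threshold is fixed at 10 x ULN. The protocol's baseline-relative threshold is 5b for b >1 to <3, and 3b for b from 3 to <5.

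- 5b < 10 only when b < 2.
- 3b < 10 only when b < 10/3 = 3.33.

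Cases that meet the baseline-relative rule but not the SAP rule:

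| Baseline (x ULN) | Protocol threshold (x ULN) | Peak not counted by the SAP (x ULN) |
|---|---|---|
| 1.1 | 5 x 1.1 = 5.5 | 5.5 to <10 |
| 1.5 | 5 x 1.5 = 7.5 | 7.5 to <10 |
| 1.9 | 5 x 1.9 = 9.5 | 9.5 to <10 |
| 3.0 | 3 x 3.0 = 9.0 | 9.0 to <10 |
| 3.2 | 3 x 3.2 = 9.6 | 9.6 to <10 |

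The difference can also run the other way. At b = 2.5 the baseline-relative threshold is 5 x 2.5 = 12.5, above the SAP's 10. If the protocol means its baseline-relative rules to replace the ULN rules, the SAP would over-count there.

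**Hepatic definition: enzyme plus bilirubin**

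The SAP requires at least 3 x ULN for the enzyme with at least 2 x ULN for bilirubin.

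- Enzyme: with b > 1, 3b > 3. With b at least 3, 2b is at least 6. Any value meeting the protocol rule therefore meets the SAP's 3 x ULN.
- Bilirubin: the protocol asks for 2 x ULN, or twice an elevated baseline, and twice a value above ULN exceeds 2 x ULN.

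No case meeting the protocol's combined baseline-relative rule is missed by the SAP. Under a replacement reading the SAP is again the wider: at b = 1.5 the protocol needs 3 x 1.5 = 4.5 x ULN, the SAP 3 x ULN.

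**The case against.** The strongest reply is that the AESI outputs may be built from the investigator's flag, so that the list in SAP 7.8.1 only describes. AESIs are documented on the CRF (protocol 5.2.6.2.1), the SAP analyses AEs as original results, and it keeps search-derived concepts separate from AESIs. On that reading a flagged neuropathy event would appear in both outputs. This is plausible, but it is an inference: the SAP nowhere says that the flag is used, and its list would still be wrong. What stands is that omission is a risk and not a certainty.

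A second reply is that protocol section 7 plans no AESI table, so SAP section 4 had nothing to declare, and what the protocol requires is expedited reporting, which the SAP leaves alone. That softens the charge of an undeclared change. It does not explain why the SAP restates a protocol definition with a class missing.

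A third is that Table 7.8.1:1 looks incomplete as extracted: one entry refers to a definition above it that is not visible, and a footnote has no anchor. That is fair, and nothing here depends on the table.

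On the liver, the uncertainty begins in the protocol, which does not say whether the baseline-relative rules add to or replace the ULN rules. Every missed window also lies above 5 x ULN, so those patients still appear in the laboratory tabulation at that cut-off in SAP 7.8.2. Both points stand and keep the liver matter secondary.

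**Conclusion.** The concern holds and should be fixed. One of five protocol AESI classes is absent from the SAP's list. Followed literally, that list removes peripheral neuropathy from the AESI summary line and the AESI table. The effect is confined to those outputs: the primary TEAE count does not change, neuropathy events remain in the SOC/PT tables, and any that are serious or lead to discontinuation remain in their own tables.

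The hepatic mismatch is real but minor. It affects isolated enzyme rises below 10 x ULN at baselines of >1 to <2 or 3 to <3.33 x ULN, and no enzyme-plus-bilirubin case is missed. Those windows compare the SAP with the baseline-relative criteria. If these replace the ULN criteria, the SAP would also over-count at other baselines.

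The conclusion rests on the visible SAP text. Parts of the SAP are redacted or not shown, but sections 4 and 7.8.1 as they stand contain nothing that resolves the difference.

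**What to change.** In SAP 7.8.1:

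1. Add peripheral neuropathy to the AESI list, with a matching search concept if Table 7.8.1:1 does not already hold one.
2. State whether the AESI summary line and AESI table use the investigator-reported flag or the SAP's own list.
3. Reconcile the hepatic injury definition with protocol 5.2.6.1.4, and have the sponsor state whether the baseline-relative criteria add to or replace the ULN criteria.
4. If any difference from the protocol is intended, declare it in SAP section 4 with the reason.

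The cost is a text edit and possibly one search concept. AESIs and liver laboratory values are already collected, so no new data are needed.
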